This study will be a Phase 1b/II single center, open-label, non-randomized clinical trial with the dual primary objectives of assessing the safety and efficacy of omacetaxine in combination with the BCL2 inhibitor venetoclax for patients with RUNX1-mutated relapsed or refractory AML or MDS. Up to 12 cycles will be administered.

Patients will be instructed to self-administer OM at home and return unused intact drug syringes to be disposed of by the study staff. Patients will be given a Research Medication Diary to record the medication taken each day. Patients will be instructed to bring the diary and any unused intact medication syringes with them to all study visits. Any unused drug will be disposed of per institutional standard practice.

4.2 Phase 1b Portion:

A maximum of 12 patients will be treated in Arm A (AML) and Arm B (MDS), respectively. Patients will be enrolled in cohorts of 3 within each arm. The starting dose in both arms will evaluate omacetaxine via subcutaneous injection at a dose of 1.25 mg/m² twice daily for 3 consecutive days on days 2-4, in combination with venetoclax 400mg orally daily on days 1-10 per treatment cycle.

The RP2D will be selected at the end of the Phase 1b portion based on safety data, in Arms A and B independently. Preliminary efficacy and PK data for each dose level may also be considered as appropriate. Once the RP2D has been identified, that Arm will transition to the respective Phase 2 portion.

Table 1 below shows the planned dose levels, with the starting dose being dose level 0. Patients treated in the Phase 1b portion that are removed from study before day 28 for any reason other than toxicity, and have not experienced DLT, will be replaced.

Table 1: Dose de-escalation for omacetaxine and venetoclax

Dose Level	omacetaxine	venetoclax
+1	1.25 mg/m ² BID days 2-4	400mg QDAY days 1-14
0 (starting dose)	1.25 mg/m ² BID days 2-4	400mg QDAY days 1-10
-1	1.25 mg/m ² BID days 2-3	400mg QDAY days 1-10
-2	1.25 mg/m ² BID days 2-3	400mg QDAY days 1-7

Dose levels outside of this table may be considered based on review of patient safety and efficacy and PK data and will be detailed in a subsequent amendment, if applicable.

4.3 Phase 2:

Up to 60 patients will be treated; up to 30 patients with AML (Arm A) and up to 30 patients with MDS (Arm B) at the recommended Phase 2 dose level. Note that based on the Phase 1b portion, the dose level for the Phase 2 portion of Arm A and Arm B may not be the same.

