Treatment cycles will begin on day 1 of each new venetoclax cycle. Patients will receive one cycle every 4-6 weeks; delays of more than 6 weeks may be allowed if determined by the investigator to be in the best interest of the patient, after discussion with the PI and documentation in the patient's medical record.

4.4 Study Duration:

4.4.1. Treatment will continue for 12 total cycles unless discontinuation occurs earlier due to relapse, unacceptable toxicity, or disease progression. Reasons for study treatment discontinuation include:

- clinically significant progressive disease at any time, or
- Possibility of undergoing allogeneic stem cell transplantation
- intercurrent illness that prevents further administration of treatment, or
- unacceptable adverse event(s), or
- patient decision for study withdrawal, or
- general or specific changes in the patient's condition that render the patient unacceptable for further treatment in the judgment of the investigator
- lack of clinical response by 6 cycles of treatment (clinical response as per Section 6.1.1 or 6.1.3 including ORR or hematologic improvement)

Patients may remain on study for the planned 12 cycles of treatment, as long as the patient continues to demonstrate clinical benefit and no excessive toxicity (i.e. no clinically significant study-drug related grade ≥ 3 toxicity).

4.4.2. Dose modifications and interruptions are permitted as necessary for the clinical benefit of the patient. If side effects or toxicity are related to one study drug only; patients may proceed with dose modification and/or discontinuation of that agent and continue treatment with the remaining study agent, if in the investigator's assessment the patient continues to demonstrate clinical benefit and all protocol-specified criteria for continuation of study treatment are met. All dose modifications should be discussed with the PI and clearly documented in the medical record. Treatment may be held as long as clinically necessary for resolution, after discussion with the PI.

For patients with study-drug related clinically significant toxicities, the following dose adjustment rules apply:

- **For Grade 0-2 non-hematological toxicities, no dose reduction is required. For grade 2 toxicities that are persistent and/or intolerable (e.g. stomatitis), patients may have a treatment interruption or dose reduction to the next lower dose level.**

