6.2.1. Definition of Dose-Limiting Toxicity

A dose-limiting toxicity (DLT) is defined as any grade 3 or higher non-hematologic adverse event or abnormal laboratory value occurring during the first cycle on study that cannot be attributed by the investigator to a clearly identifiable cause such as disease progression, underlying illness, concurrent illness, or concomitant medication, with the following exceptions:

- Grade 3 nausea, vomiting or diarrhea that can be managed to < Grade 3 within 7 days with standard antiemetic or antidiarrheal medications
- Grade 3 or 4 electrolyte abnormalities will only be considered DLT if possibly related to study drug, extend beyond 72 hours, and are not corrected by optimal replacement therapy. Venetoclax interruption for up to 72 hours following transient (< 48 hours) chemical changes and laboratory TLS may be allowed and may not be considered a DLT.

Confirmed Hy's law cases will be considered as DLT. A positive Hy's law case is defined as AST or ALT $\geq 3 \times$ ULN in the setting of total bilirubin $\geq 2 \times$ ULN, without findings of cholestasis, and no other reason can be found to explain the combination of increased aminotransferases and total bilirubin, such as viral hepatitis A, B, or C, preexisting or acute liver disease, or another drug capable of causing the observed injury.

Hematologic DLT is defined as Grade ≥ 4 neutropenia and/or thrombocytopenia and no greater than 5% marrow blasts lasting for 6 weeks or more after the start of a course in the absence of underlying MDS. Anemia will not be considered for the definition of DLT.

Patients with neutropenia or thrombocytopenia as a consequence of the disease prior to the start of therapy do not require treatment interruptions for myelosuppression. Dose reductions of the study treatment in these patients may be considered on an individual case basis and discussed with the PI.

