8.0 STATISTICAL CONSIDERATIONS

This is an open label, Phase 1b/2 trial to determine the safety/tolerability (phase 1b) and preliminary efficacy (phase 2) of omacetaxine in combination with venetoclax for patients with relapsed/refractory acute myeloid leukemia or myelodysplastic syndrome harboring a *RUNX1* mutation.

Phase 1b: A maximum of 24 patients will be enrolled into this part of the study, with up to 12 patients in each arm (AML or MDS). The dose levels are show in Table 1 and the starting dose is dose level 0.

Dose limiting toxicity (DLT) will be graded according to the NCI Common Terminology Criteria for Adverse Events (CTCAE v5) by organ system. DLTs (see 6.2.1 of the protocol) that occurred within the first 1 cycle after treatment will be used for dose escalation/de-escalation decisions. The Bayesian Optimal Interval (BOIN) design (Liu and Yuan, 2015) will be used to determine the MTD of the combination for each arm. The BOIN design identifies the MTD through minimizing the incorrect decisions of dose escalation and de-escalation (i.e., erroneously escalating/deescalating the dose when the current dose is actually higher/lower than the MTD), thereby optimizing the dose assignment for each enrolled patient. The BOIN design is simple to implement and has been shown to have superior performance through simulations. The BOIN design is algorithm-based, which is similar to the traditional “3+3”; however its overall performance is substantially better.

The following design detail applies to each arm separately. The target toxicity rate for the MTD is $\phi = 0.3$. For each arm, we will enroll and treat patients in cohorts of size 3. To guide dose-escalation decisions, if the observed DLT rate at the current dose is ≤ 0.236 , the next cohort of patients will be treated at the next higher dose level; if it is ≥ 0.359 , the next cohort of patients will be treated at the next lower dose level. These boundaries were created when minimizing decision errors such that $\varphi_1 = 0.18$ is the highest toxicity probability that is considered sub-therapeutic (underdosing) and $\varphi_2 = 0.42$ is the lowest toxicity probability that is deemed overly toxic (overdosing). For the purpose of overdose control, doses j and higher levels will be eliminated from further examination if $\Pr(p_j > 0.3 | \text{data}) > 0.95$, where p_j is the true DLT rate of dose level $j, j = -2, -1, 0, 1$. When the lowest dose is eliminated, stop the trial for safety.

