8.4.2. Efficacy Evaluable Population

All patients who complete at least one post-baseline disease status assessment or who discontinue study medication early due to study drug-related toxicity will be considered evaluable for efficacy. Patients who do not meet the aforementioned requirements will be considered non-evaluable for response and may be replaced.

In addition, we will perform a sensitivity analysis for the efficacy endpoint which will include all patients who have received at least one dose of the study treatment (i.e., those who drop off study early due to any reason will be counted as non-responders).

8.4.3. DLT-evaluable population:

Unless doses are missed in Cycle 1 due to DLT(s), a patient must receive at least 70% of the planned doses of venetoclax and omacetaxine to be considered evaluable for DLT. If a patient received fewer doses/days of treatment in the first cycle of treatment for reasons other than a DLT, the patient will be considered non-evaluable for DLT and replaced.

8.5 Analysis Plan:

Descriptive statistics including plots, mean, median and standard deviations will be used to summarize data. For the primary efficacy analysis, we will estimate the ORR for the combination treatment, along with the Bayesian 95% credible interval. The priors for ORR will be (0.2, 0.8) for AML cohort and (0.15, 0.85) for MDS cohort. Event-free survival (EFS) is defined as the time interval between the date of treatment start and the date of [treatment failure, relapse or death from any cause](#). The Kaplan-Meier method will be used to estimate the probabilities of event-free survival (EFS) and overall survival (OS). Log-rank tests will be used to compare among subgroups of patients in terms of EFS or OS. Similar analyses will be performed for the duration of response. MRD negative status and exploratory biomarkers will be summarized graphically and with descriptive statistics. The association between molecular and cellular markers and overall response and/or resistance will be assessed through logistic regression analyses. Paired t-test or Wilcoxon signed rank test will be used to assess the marker change over time. Safety data will be summarized using frequency and percentage, by category and severity.

The Investigator is responsible for completing an efficacy/safety summary report, and submitting it to the IND Office Medical Affairs and Safety Group, for review and approval

- Phase 1b

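### Section 8.4.3 drops and replaces a patient who missed Cycle 1 doses for a non-DLT reason and separately had a DLT, so that DLT leaves the BOIN count

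*Combined protocol and SAP*

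**What the plan says.** Section 8.4.3 (DLT-evaluable population) has two parts. The requirement carries an exemption: "Unless doses are missed in Cycle 1 due to DLT(s), a patient must receive at least 70% of the planned doses" of venetoclax and omacetaxine. The consequence follows for a patient who received less in the first cycle: "for reasons other than a DLT, the patient will be considered non-evaluable for DLT and replaced". Both parts turn on the reason for the missed doses.

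Section 4.2 has its own replacement rule. Phase 1b patients "removed from study before day 28 for any reason other than toxicity, and have not experienced DLT, will be replaced".

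The DLT window is the whole first cycle. Section 6.2.1 defines a DLT as an event "occurring during the first cycle on study that cannot be attributed by the investigator to a clearly identifiable cause", with listed exceptions, and Section 8.0 says that DLTs "within the first 1 cycle after treatment will be used for dose escalation/de-escalation decisions". The BOIN decision table in Section 8.0 (the first of two tables numbered 4) counts patients who have one or more DLTs.

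On timing, Section 4.2 gives omacetaxine at the starting level "twice daily for 3 consecutive days on days 2-4", "in combination with venetoclax 400mg orally daily on days 1-10 per treatment cycle". The cycle length is stated under Section 4.3: "Patients will receive one cycle every 4-6 weeks".

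**The concern.** Consider a patient who misses doses early in Cycle 1 for a reason that is not a DLT, such as a tolerability hold, a lapse in self-administration at home or a supply problem, and who later in the same cycle has an event meeting Section 6.2.1. The exemption in 8.4.3 does not reach this patient, because the doses were not missed due to the DLT. The replacement clause does. An observed DLT is then set aside and the place is filled by someone else.

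Each arm has at most 12 patients in Phase 1b, in cohorts of 3, so a single DLT often decides the next dose level. A DLT seen on less than the planned exposure is not normally evidence that a dose-finding rule should ignore.

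**Working it through.** **1. The case can arise.** At level 0 omacetaxine ends on day 4 and venetoclax on day 10, while the DLT window runs for the whole cycle (4-6 weeks). Most of the window therefore follows the last planned dose. A haematologic DLT under 6.2.1 needs cytopenia lasting 6 weeks or more from the start of the course, long after any dose missed by day 10.

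**2. The 70% threshold.** Level 0 plans 3 x 2 = 6 omacetaxine doses and 10 venetoclax doses.
- Per drug: 0.70 x 6 = 4.2, so at least 5 of 6; 0.70 x 10 = 7. One missed omacetaxine day gives 4/6 = 67%, below the threshold.
- Pooled: 0.70 x 16 = 11.2, so at least 12 of 16. The same missed day gives 14/16 = 87.5%, above it.

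8.4.3 does not say which reading applies.

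**3. The two replacement rules.**
- Below 70% for a non-DLT reason, had a DLT, removed before day 28 for a non-toxicity reason: replaced under 8.4.3, outside the group that 4.2 replaces.
- Same patient, not removed: replaced under 8.4.3; 4.2 does not address the case.
- Below 70% because of toxicity short of a DLT, and removed for it before day 28: replaced under 8.4.3, outside the group that 4.2 replaces.

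**4. The plan's BOIN figures reproduce.** With target 0.30, phi1 = 0.18 and phi2 = 0.42:
- escalation boundary = ln(0.82/0.70) / ln[(0.30 x 0.82)/(0.18 x 0.70)] = 0.2365 (stated 0.236)
- de-escalation boundary = ln(0.70/0.58) / ln[(0.42 x 0.70)/(0.30 x 0.58)] = 0.3585 (stated 0.359)

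All 27 entries of the decision table match, with elimination from a Beta(1,1) prior. In 20,000 simulated trials, scenario 3 selection at levels -2/-1/0/+1 was 0.2/19.9/54.4/25.3%, against the stated 0.3/19.3/54.5/25.6%. The match is best when the 9-patient stop applies only if the decision is to stay.

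**5. One DLT discarded, replacement without a DLT.**

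| Counted in full | Decision | After discard | Decision |
|---|---|---|---|
| 1/3 | stay | 0/3 | escalate |
| 2/3 | de-escalate | 1/3 | stay |
| 3/3 | eliminate | 2/3 | de-escalate |
| 2/6 | stay | 1/6 | escalate |
| 3/6 | de-escalate | 2/6 | stay |

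Not every count is affected: 1/6 escalates either way.

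**6. How often.** Let q be the share under-dosed for non-DLT reasons and d the DLT rate among them. The documents give neither; q = 5%, 10%, 20% and d = 0.30 are assumptions. The chance of at least one discarded DLT among 12 patients is 1 - (1 - qd)^12:
- q = 5%: 1 - 0.985^12 = 17%
- q = 10%: 1 - 0.97^12 = 31%
- q = 20%: 1 - 0.94^12 = 52%

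**7. What keeping these DLTs does.** With p the DLT rate in adequately dosed patients, the expected rate as written is p. If under-dosed patients are kept only when they had a DLT, it is [(1 - q)p + qd] / [(1 - q) + qd]. With p = d = 0.30:
- q = 10%: 0.30/0.93 = 0.323
- q = 20%: 0.30/0.86 = 0.349

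In simulation with q = 20% and d = p, taking the scenario rates as those of adequately dosed patients, scenario 3 selection of level +1 (rate 0.47) falls from 25.3% to 14.7%. Level -1 (rate 0.13) rises from 19.9% to 29.4%, and level 0 (rate 0.30) is nearly unchanged, 54.4% against 55.1%.

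**The case against.** A reader might infer that every under-dosed patient with a DLT is lost. The text does not support that: the exemption in 8.4.3 keeps the commonest case, where the DLT itself cut dosing short.

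A reader might also infer a flat contradiction with 4.2. That section speaks only of patients removed before day 28, and it lists who is replaced without saying that nobody else may be. The rules are unaligned where they overlap, and no more than that.

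The strongest objection concerns bias. The rule discards under-dosed patients without a DLT as well. At q = 10% and d = 0.30 in 12 patients, that is 12 x 0.10 x 0.70 = 0.84 expected patients without a DLT, against 12 x 0.10 x 0.30 = 0.36 with one. If under-dosed patients have the same DLT rate as the rest, the expected rate as written stays at 0.30, so the documents do not show a systematic push toward escalation. The rule understates the all-treated rate only if d exceeds p. For example, q = 20% and d = 0.45 give 0.80 x 0.30 + 0.20 x 0.45 = 0.33 against 0.30. It is the fix that moves the expected rate upward. This objection stands.

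Two further limits also stand. The shifts in step 5 need a replacement without a DLT; at a 30% rate the replacement has one 30% of the time. And that one missed omacetaxine day breaches the threshold holds only on the per-drug reading.

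There are partial safeguards. The event remains in the safety population (8.4.1), RP2D selection draws on safety data more broadly (4.2, 8.0), and the IND Office must approve dose changes (8.5). Decision-makers can therefore see the DLT, but none of these puts it back into the BOIN count.

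**Conclusion.** The point holds in a narrow form. As written, 8.4.3 makes non-evaluable, and replaces, a patient who fell below 70% for a non-DLT reason and separately had a Cycle 1 DLT. That is a stated rule with a poor consequence, not a missing detail.

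One such case can move the dose decision one step upward. The 17% to 52% chance per 12 patients rests on assumed under-dosing of 5% to 20% and an assumed 30% DLT rate; at 10% under-dosed, about 69% of 12-patient arms would have no such case.

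The argument for change is that an observed DLT should count in a small dose-finding arm, not that the written rule has been shown to be biased. The stated BOIN boundaries, decision table and operating characteristics are not in question. This is a cheap improvement.

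**What to change.** In 8.4.3, state three things:
- Any patient with a DLT in Cycle 1 is DLT-evaluable, whatever share of the planned doses was received.
- The 70% requirement, and replacement for failing it, apply only to patients without a DLT.
- Whether the 70% applies to each drug separately or to all planned doses together.

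Make 4.2 refer to 8.4.3 as the single replacement rule. That also settles the case of a patient removed for toxicity short of a DLT.

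The cost is a few sentences: no added patients, slightly fewer replacements, and no change to the BOIN boundaries or decision table. The price is deliberate conservatism. If under-dosed patients have the same DLT rate as the others, the expected observed rate at a true 0.30 rises to about 0.32 with 10% under-dosed and 0.35 with 20%, and lower levels are selected somewhat more often. The protocol should acknowledge that this is intended.

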In the New York Medical College studies, Feldman et al. used OM, 5 mg/m², by continuous infusion daily for 9 days in patients with refractory-recurrent acute leukemia or blastic phase CML.(Feldman et al., 1992) Sixty-six patients were treated; their median age was 41 years. CRs were achieved in 7 of 43 patients (16%) with recurrent AML, in none of 11 patients with AML that primarily was resistant to anthracycline-cytarabine combinations, and in 2 of 3 patients whose disease was resistant to low-dose cytarabine. Side effects included significant hypotensive events, fluid retention, weight gain (29%), and hyperglycemia (63%). Other studies have also demonstrated the activity of OM in AML.

Given the excellent bioavailability of subcutaneous OM and its ability to be administered in the outpatient setting, OM was subsequently developed as a treatment for CML. Based on promising clinical activity in several phase II studies, OM was granted U.S. Food and Drug Administration approval in October 2012 for treatment of adults with chronic- or accelerated-phase CML who are resistant and/or intolerant to two or more tyrosine kinase inhibitors.

Recently, a trial of low-dose omacetaxine for patients with relapsed MDS was performed at our institution at a dose of 1.25 mg/m² subcutaneously twice daily on a 3 day schedule.(Short et al., 2019) Forty two patients were enrolled, with a median age of 76 years. The ORR was 33%, with a median OS of 7.5 months. The most common grade ≥ 3 adverse events were infections (26%), febrile neutropenia (10%), and hemorrhage (7%) Of importance, two patients had ongoing response to OM lasting 2 years or longer, and both patients were noted to have RUNX1 mutations.

We have recently also reported our experience using OM for 3 days in combination with low-dose cytarabine. This combination was found to be safe and effective in inducing an objective response rate of 50% (CR rate of 30%) with a median survival of 9.3 months.

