After Phase 1b part of the trial is completed, select the MTD for each arm based on isotonic regression as specified in Liu and Yuan (2015). This computation is implemented by the shiny app "BOIN" available at <http://www.trialdesign.org>. Specifically for each arm, select as the MTD the dose for which the isotonic estimate of the toxicity rate is closest to the target toxicity rate. If there are ties, select the higher dose level when the isotonic estimate is lower than the target toxicity rate and select the lower dose level when the isotonic estimate is greater than or equal to the target toxicity rate. Furthermore, the RP2D will be selected based on safety and efficacy, in Arms A and B independently.

Operation Characteristics

Table 3 shows the operating characteristics of the Boin design based on 1000 simulations using shiny app "BOIN" available at <http://www.trialdesign.org>. The operating characteristics show that the design selects the true MTD, if any, with high probability and allocates more patients to the dose levels with the DLT rate closest to the target of 0.3.

Table 3. Operating characteristics of the Boin design (Dose 0 is the starting dose)

	Dose Level -2	Dose Level -1	Dose Level 0 (starting dose)	Dose Level 1	Number of Patients	% Early Stopping
Scenario 1						
True DLT Rate	0.47	0.55	0.64	0.75		
Selection %	44.2	27.6	8.2	0.1		19.9
% Pts Treated	24.4	36	37.7	1.9	11.8	
Scenario 2						
True DLT Rate	0.11	0.3	0.47	0.67		
Selection %	9.1	52.5	34.3	3.2		0.9
% Pts Treated	5.8	33.8	52	8.4	11.8	
Scenario 3						
True DLT Rate	0.02	0.13	0.3	0.47		
Selection %	0.3	19.3	54.5	25.6		0.3
% Pts Treated	0.4	15.7	58.1	25.9	11.7	
Scenario 4						
True DLT Rate	0.05	0.1	0.15	0.3		
Selection %	0	2.4	26.6	71		0
% Pts Treated	0	3.1	43.8	53.2	11.9	

Phase II:

In phase II portion of the study, patients will be treated at the RP2D level chosen during phase 1b for each arm separately. A maximum of 30 patients will be treated in each arm. For AML patients, the primary efficacy endpoint is overall response, defined as CR, CRh, CRi, PR or marrow clearance of blasts within 3 cycles of treatment. For MDS patients, the primary efficacy endpoint is overall response, defined as CR, PR, HI (Hematologic Improvement), or mCR (marrow clearance of blasts) within 3 cycles of treatment. In addition, we will continue to monitor the DLTs that occurred during the first 3 cycles of treatment.

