For each arm, the efficacy and toxicity will be monitored simultaneously using the Bayesian optimal phase 2 (BOP2) design (Zhou, Lee and Yuan, 2017). Specifically, let n denote the interim sample size and N denote the maximum sample size. Let Y_{eff} and Y_{tox} denote the binary efficacy and toxicity endpoints, with $Y_{eff} = 1$ and $Y_{tox} = 1$ indicating that patients experience efficacy and toxicity, respectively. We assume that the joint distribution of (Y_{eff}, Y_{tox}) follows a multinomial distribution with four elementary outcomes: $(Y_{eff}, Y_{tox}) = (1, 1), (1, 0), (0, 1)$ and $(0, 0)$. Let $\mathbf{p} = (P_{11}, P_{10}, P_{01}, P_{00})$ denote the probabilities of observing the four outcomes, and let $p_{eff} = Pr(Y_{eff} = 1)$, $p_{tox} = Pr(Y_{tox} = 1)$ and $p_{efftox} = Pr(Y_{eff} = 1, Y_{tox} = 1)$.

AML Arm:

The treatment is deemed unacceptable if $p_{eff} \leq 0.2$ or $p_{tox} > 0.2$. Thus, we will stop enrolling patients and claim that the treatment is unacceptable if

$$Pr(p_{eff} > 0.2 | data) < \lambda \left(\frac{n}{N} \right)^\alpha,$$

or

$$Pr(p_{tox} \leq 0.2 | data) < \lambda \left(\frac{n}{N} \right)^{\alpha/3},$$

where $\lambda=0.5$ and $\alpha=0.51$ are design parameters optimized to maximize the study power, i.e., probability of correctly concluding an efficacious and safe treatment as acceptable when $p_{eff} = 0.4$, $p_{tox} = 0.1$ and $p_{efftox} = 0.04$, while controlling that the probability of incorrectly claiming an ineffectual and toxic treatment, i.e., type I error, with $p_{eff} = 0.2$, $p_{tox} = 0.2$ and $p_{efftox} = 0.04$, to 10.4%. Note that in the safety stopping rule, the original publication of the design used the probability cutoff $\lambda(n/N)^\alpha$, here the attenuation factor 3 is added (i.e., $\alpha/3$) to obtain stricter interim stopping boundaries to enhance safety.

This optimization is performed assuming a vague Dirichlet prior $Dir(0.04, 0.16, 0.16, 0.64)$ for \mathbf{p} . The prior is chosen such that it corresponds to a prior effective sample size of 1 patient, and the prior estimates of p_{eff} and p_{tox} match the values specified when the treatment is unacceptable. The above decision rule leads to the following optimal stopping boundaries, in cohort size of 6.

Table 4: Optimized stopping boundaries for AML Arm

# patients treated	Stop if # response <=	OR # toxicity >=
6	0	2
12	1	3
18	3	4
24	4	6
30	6	7

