When the total number of AML patients reaches the maximum sample size of 30, we conclude that the treatment is acceptable if the number of responses are greater than 6, and the number of toxicities are less than 7; otherwise we conclude that the treatment is unacceptable. The go/no-go criteria in Table 4 are non-binding.

Below are the operating characteristics of the design based on 10000 simulations using the BOP2 web application (BOP2 V1.4.7.0), which is available at <http://www.trialdesign.org>.

Table 5: Operating characteristics for the interim futility and toxicity monitoring in AML Arm

Scenario	Pr(Eff)	Pr(Tox)	Pr(Eff & Tox)	Early Stopping (%)	Claim Acceptable (%)	Average Sample Size
1	0.20	0.20	0.040	85.03	10.44	12.8
2	0.40	0.10	0.040	25.31	73.93	24.8
3	0.40	0.25	0.120	80.66	15.88	13.4
4	0.15	0.30	0.045	98.07	0.77	8.5

MDS Arm:

The treatment is deemed unacceptable if $p_{eff} \leq 0.15$ or $p_{tox} > 0.2$. Thus, we will stop enrolling patients and claim that the treatment is unacceptable if

$$Pr(p_{eff} > 0.15 | data) < \lambda \left(\frac{n}{N} \right)^\alpha,$$

or

$$Pr(p_{tox} \leq 0.2 | data) < \lambda \left(\frac{n}{N} \right)^{\alpha/3},$$

where $\lambda=0.52$ and $\alpha=0.15$ are design parameters optimized to maximize the study power, i.e., probability of correctly concluding an efficacious and safe treatment as acceptable when $p_{eff} = 0.3$, $p_{tox} = 0.1$ and $p_{efftox} = 0.03$, while controlling that the probability of incorrectly claiming an ineffectual and toxic treatment, i.e., type I error, with $p_{eff} = 0.15$, $p_{tox} = 0.2$ and $p_{efftox} = 0.03$, to 9.8%. Note that in the safety stopping rule, the original publication of the design used the probability cutoff $\lambda(n/N)^\alpha$, here the attenuation factor 3 is added (i.e., $\alpha/3$) to obtain stricter interim stopping boundaries to enhance safety.

This optimization is performed assuming a vague Dirichlet prior $Dir(0.03, 0.12, 0.17, 0.68)$ for \mathbf{p} . The prior is chosen such that it corresponds to a prior effective sample size of 1 patient, and the prior estimates of p_{eff} and p_{tox} match the values specified when the treatment is unacceptable. The above decision rule leads to the following optimal stopping boundaries, in cohort size of 6.

Table 6: Optimized stopping boundaries for MDS Arm

# patients treated	Stop if # response \leq	OR # toxicity
		\geq
6	0	2
12	1	3
18	2	4
24	3	5
30	4	7

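### The priors for the reported ORR interval concentrate near zero, so an arm stopped with very few responses, chiefly 0/6, would report too low an upper limit

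*Combined protocol and SAP*

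**What the plan says.** Section 8.5 (Analysis Plan) describes the primary efficacy analysis as follows: "we will estimate the ORR for the combination treatment, along with the Bayesian 95% credible interval". The next sentence gives the priors: "The priors for ORR will be (0.2, 0.8) for AML cohort and (0.15, 0.85) for MDS cohort". Neither the distribution family nor the type of interval (equal-tailed or highest posterior density) is named.

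The same number pairs underlie the Phase II monitoring in Section 8.0. For each arm the text says "This optimization is performed assuming a vague Dirichlet prior", with parameters (0.04, 0.16, 0.16, 0.64) for AML and (0.03, 0.12, 0.17, 0.68) for MDS. The stated reason is that "it corresponds to a prior effective sample size of 1 patient" and that the prior means equal the rates at which treatment is judged unacceptable. No separate reason is given for using these priors to report the result.

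Each arm has looks at 6, 12, 18, 24 and 30 patients, and the go/no-go criteria are described as non-binding. On sample size: "A maximum of 30 patients will be treated in each arm".

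**The concern.** A prior worth one patient sounds harmless, and with 30 patients it nearly is. Its shape matters when an arm stops at six. A Beta density with first parameter 0.2 or 0.15 rises without bound at zero. If no responses are seen, nothing in the data pulls the posterior away from that spike, and the upper limit falls well below what six patients can support.

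The spike is also hard to defend as a belief. The design's own unacceptable rates are 20% and 15%. For relapsed MDS, Section 2.2.1 reports of low-dose omacetaxine alone: "The ORR was 33%, with a median OS of 7.5 months". A 48% prior probability that the combination's MDS response rate is below 1% does not fit that.

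At stake is the published primary estimate of an arm that stops early. It could appear to rule out rates that its data do not rule out.

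**Working it through.** **Inputs.** Priors are from Section 8.5. Dirichlet parameters, boundaries and operating characteristics are from the Phase II part of Section 8.0. Null and target ORR are 0.20 and 0.40 (AML), 0.15 and 0.30 (MDS). The target toxicity rate is 0.10. Futility limits (stop at or below) at the five looks are 0/1/3/4/6 for AML and 0/1/2/3/4 for MDS. Toxicity limits (stop at or above) are 2/3/4/6/7 and 2/3/4/5/7.

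**Step 1: the Beta reading.** The efficacy marginal of the Dirichlet is Beta(P11 + P10, P01 + P00).
- AML: 0.04 + 0.16 = 0.20 and 0.16 + 0.64 = 0.80.
- MDS: 0.03 + 0.12 = 0.15 and 0.17 + 0.68 = 0.85.

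These match the pairs in Section 8.5.

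**Step 2: reproduce the plan's figures.** Posterior Beta tails compared with λ(n/N)^α for efficacy and λ(n/N)^(α/3) for toxicity return all ten printed boundary rows. Exact enumeration of the (response, toxicity) paths gives:

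| Arm | Type I error, computed (stated) | Power, computed (stated) |
|---|---|---|
| AML | 10.25% (10.44%) | 74.05% (73.93%) |
| MDS | 9.25% (9.77%) | 64.96% (65.36%) |

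The stated values come from 10,000 simulations (standard error about 0.3 points for the type I errors), so they agree.

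**Step 3: prior mass near zero.** P(ORR < 0.01) is 0.373 under Beta(0.2, 0.8) and 0.483 under Beta(0.15, 0.85).

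**Step 4: the interval after 0/6.** The posterior is Beta(0.2, 6.8) for AML and Beta(0.15, 6.85) for MDS. It puts 62% and 70% of its mass below 1%. The upper limit is the 97.5th percentile:
- AML 21.0%, MDS 17.9%.
- Beta(1,1) prior: 41%.
- Clopper-Pearson: 1 − 0.025^(1/6) = 45.9%.

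The chance of 0/6 is 0.8^6 = 26% at a true ORR of 20%, 0.7^6 = 12% at 30% and 0.6^6 = 5% at 40%. So the MDS interval would exclude 20% on a result seen in a quarter of arms at that rate.

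**Step 5: coverage with the stops obeyed.** For each final (n, responses), form the equal-tailed 95% interval and sum the probabilities of the outcomes whose interval contains the true ORR. Toxicity rate 0.10, endpoints independent.

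| Arm | True ORR | Plan's interval | Clopper-Pearson |
|---|---|---|---|
| AML | 20% (null) | 97.7% | 98.9% |
| AML | 21% | 74.2% | 98.5% |
| AML | 25% | 80.3% | 98.1% |
| AML | 30% | 82.2% | 98.4% |
| AML | 40% (target) | 89.3% | 96.5% |
| MDS | 15% (null) | 97.8% | 99.0% |
| MDS | 18% | 68.4% | 98.8% |
| MDS | 20% | 71.5% | 98.9% |
| MDS | 25% | 80.3% | 98.1% |
| MDS | 30% (target) | 81.3% | 98.4% |

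Between the tabulated points coverage peaks at just under 90% in AML (at 39%) and about 83% in MDS (at 27%). The drop just above each null occurs where the true rate passes the 0/6 upper limit.

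**Step 6: what drives it.** Stopping at 0/6 accounts for 17.8 of the 19.7 points of non-coverage at AML 25%, 26.2 of 28.5 at MDS 20%, and 11.8 of 18.7 at MDS 30%. The misses are one-sided: at MDS 30%, the upper limit is below the truth in 17.1% of trials and the lower limit above it in 1.6%. Under identical stopping Clopper-Pearson stays at 96.5% or more, so the prior, not stopping alone, causes the shortfall.

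**Step 7: full enrolment.** At a fixed n = 30 without interim looks, the plan's interval covers about 91-97% from null to target in both arms.

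**Step 8: interval type.** With highest-posterior-density limits, the 0/6 upper limits are 14.8% (AML) and 12.0% (MDS). Coverage with stops obeyed is then 73-89% in AML and 61-81% in MDS from null to target.

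**The case against.** The strongest reply is that nothing in the plan is miscalculated. A credible interval states posterior probability under a declared prior; the documents promise no repeated-sampling coverage. The prior's weight and centre are justified openly, and using one prior for monitoring and reporting is coherent. Decisions rest on counts, so the interval changes none of them. All of this stands, and it makes this a point about the choice of prior.

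A reader might infer more than the documents support:
- **That the interval under-covers at every rate of interest.** It does not: at the null rates coverage is about 98%, and at a fixed 30 patients it is close to nominal.
- **That every early-stopped arm is affected.** An arm stopped for toxicity at 1/6 gets 0.9-50.1% (AML) or 0.7-49.1% (MDS), which includes the target. The problem belongs to stops with very few responses.
- **That the coverage figures describe the trial as it will run.** The criteria are non-binding, so actual coverage lies between the two calculations. An arm that does stop at 0/6 still reports the low limit.
- **That the 33% ORR contradicts both priors.** It is an MDS result. The AML single-agent figures in Section 2.2.1 are lower (for example 14 CRs among 91 evaluable patients), and an AML prior mean of 20% does not conflict with them.

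What the reply does not answer is the shape of the prior. Matching the mean and weight for a stopping rule does not justify placing 37% or 48% of belief below 1% when reporting the result.

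**Conclusion.** The concern holds for arms that stop with very few responses. After 0/6 the reported upper limit would be 21.0% (AML) or 17.9% (MDS), where the exact limit is 46%. With the stops followed, coverage is about 74-90% for AML rates from 21% to the target and about 68-83% for MDS rates from 18% to the target.

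This rests on the Beta reading, equal-tailed limits, a toxicity rate of 0.10, independent endpoints and every stop being obeyed. Few-response stops are a realistic prospect: at the target rates the plan's own Tables 5 and 7 give early stopping, for futility or toxicity, in 25.31% (AML) and 34.21% (MDS) of trials. The stopping rules are unaffected.

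**What to change.** In Section 8.5:
1. Keep the Dirichlet priors for the BOP2 boundaries only.
2. Report the observed ORR in each arm with an exact (Clopper-Pearson) 95% interval, in place of the credible interval or beside it.
3. If a credible interval is kept, name the Beta family and say whether it is equal-tailed or highest posterior density.

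Clopper-Pearson is preferable to a credible interval under Beta(1,1), whose coverage falls to about 92% at an AML ORR of 45%. Clopper-Pearson makes no allowance for the interim looks, but under the printed boundaries its coverage stays at about 94% or more for ORRs from 10% to 60%.

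The cost is a sentence or two and wider intervals, chiefly in early-stopped arms. At full enrolment the change is small: for 12/30 in AML, 23.2-56.8% becomes 22.7-59.4%, the latter from the 2.5th percentile of Beta(12, 19) and the 97.5th of Beta(13, 18). The boundary and operating-characteristic tables (Phase II Tables 4-7) and all decisions stay as they are.
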